## 1.0 BACKGROUND AND HYPOTHESES

### 1.1 Background:

Postoperative constipation is among the most common complaints among women after gynecologic surgery. In the early postoperative period a temporary delay in gastrointestinal motility can be expected secondary to manual manipulation of bowel and medications including anesthesia and opiates. Postoperative constipation is a significant problem as return of bowel function is the most common reason for delayed hospital discharge after abdominal surgery. Without intervention, the average time to bowel movement after benign gynecologic and urogynecologic surgery is 4 days +/- 1.5 days. Delayed time to first bowel movement after surgery is often associated with patient discomfort and contributes to a delay in postoperative recovery.

The exact pathophysiology of delayed return of bowel function is unknown. Bayliss and Starling described the presence of inhibitory spinal reflexes acting on the bowel in 1899, which were later identified to be sympathetic inhibitory pathways in the autonomic nervous system. Sympathetic inhibition involves prevention of acetylcholine release from excitatory fibers in the myenteric plexus. The enteric nervous system has also been implicated as Holzer and Lippe suggested the role of Substance P, a neurotransmitter associated with pain. Bult et al. proposed that nitric oxide is the major inhibitory nonadrenergic noncholinergic neurotransmitter in the enteric nervous system. Hormones and neuropeptides such as vasoactive intestinal peptides, inflammation mediated by macrophages and neutrophils, general anesthesia and opioid narcotics may also contribute to the pathophysiology of delayed return to bowel function after surgery.

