## 2.0 OBJECTIVES AND PURPOSE

2.1 To determine the time to first bowel movement after benign gynecological surgery in women treated with prunes and docusate compared to those treated with docusate alone.

2.2 To determine pain associated with first bowel movement (scale 1-10), stool consistency using Bristol stool form scale, the need for additional laxatives, compliance and patient satisfaction.

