#### 10.0 CRITERIA FOR EVALUATION AND ENDPOINT DEFINITIONS

The outcome status of all eligible patients will be reported. All eligible patients who begin treatment will be included in the analysis.

Primary endpoints: Time to first bowel movement (in hours)

Secondary endpoints:

1. Stool consistency of the first bowel movement as classified by the Bristol Stool Scale (The stool types are categorical variables, and we will evaluate the differences in the frequencies of the responses by treatment status with a chi-square test)
2. Pain with bowel movement measured (Likert scale, and assessed using t-test or non-parametric methods as appropriate)
3. Satisfaction with bowel regimen (Likert scale, and assessed using t-test or non-parametric methods as appropriate)
4. Satisfaction with surgery overall (Likert scale, and assessed using t-test or non-parametric methods as appropriate)
5. Requirements for laxative (yes or no, assessed as categorical variables and evaluated by chi-square test)
6. Compliance with docusate (percentage of medications consumed, and assessed using t-test or non-parametric methods as appropriate)
7. Compliance with prunes (percentage of prunes consumed, and assessed using t-test or non-parametric methods as appropriate)

8. Adverse events of extreme bloating or flatulence (yes or no, assessed as categorical variables and evaluated by chi-square test)

Compliance with prune consumption will be defined as reported successful consumption of 2/3 of the assigned prunes.

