#### 13.0 STATISTICAL CONSIDERATIONS

The sample size of 63 participants per treatment group was calculated to detect a clinically significant mean difference in time to first bowel movement of 12 hours using a two-sample t-test with a standard deviation of 23.7 at 80% power and two-sided significance level of  $p=0.05$ . The sample size was inflated to 70 participants per group to account for an estimated 10% attrition rate.

Summaries of participant characteristics will be described by treatment arm. Participant characteristics will be presented as means and standard deviations for continuous variables and counts and percentages for categorical variables. Comparisons of baseline characteristics will be assessed using two-sample t-tests or the non-parametric corollary for continuous variables and chi-square test for categorical variables. The primary outcome, a comparison of the time to first bowel movement between the treatment and control groups, will be assessed using two-sample t-tests. The secondary outcome, pain at first BM, will also be evaluated using two sample t-tests.

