# Prunes Data Collection Sheet

## Self administered survey

Have you had a bowel movement since surgery? Yes No

If Yes, When did you have your first bowel movement?

Date \_\_\_\_\_ Time \_\_\_\_\_

How *painful* was your first bowel movement?

Not at all painful 0    1    2    3    4    5    6    7    8    9    10 Very painful

Which picture best describes your bowel movement (Circle one number)?

1    2    3    4    5    6    7

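### The ordered Bristol type of the first stool is tested only by an unordered chi-square, with no fixed grouping, effect estimate or interval

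*Combined protocol and SAP*

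**What the plan says.** Objective 2.2 lists "stool consistency using Bristol stool form scale" among the secondary aims, with no direction or cut-point. The chart in Appendix III runs in order from type 1 (hard and difficult to pass) to type 7 (wholly liquid), and the woman circles one number.

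Section 10.0, secondary endpoint 1, declares the types categorical and names one analysis: "we will evaluate the differences in the frequencies of the responses by treatment status with a chi-square test". Section 13.0 mentions only one secondary outcome, and it is a different one: "The secondary outcome, pain at first BM, will also be evaluated using two sample t-tests".

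The neighbouring endpoints are handled differently. Endpoints 2 to 4 are ordered 0-10 ratings and get methods that use the order, for example "Pain with bowel movement measured (Likert scale, and assessed using t-test or non-parametric methods as appropriate". Endpoint 5 is binary: "Requirements for laxative (yes or no, assessed as categorical variables and evaluated by chi-square test". With two levels there is no order to lose. Endpoint 1 is the only ordered, multi-level outcome given a test that ignores order.

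**The concern.** Two things are lost when an ordered scale is tested as unordered.

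- **Power.** A seven-type table spends six degrees of freedom on every possible pattern of difference. If prunes move stools consistently softer, most of that is wasted, and a real shift is more likely to be reported as no difference in consistency.
- **Interpretation.** Fewer hard stools is a benefit. More loose stools may be a harm: section 8.1 names diarrhea as a possible effect, while adverse-event endpoint 8 covers only severe bloating or gas. A significant chi-square fits either change. With no grouping written down, a later statement about hard or loose stools would rest on a cut chosen after the counts were known, with no planned interval around it.

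**Working it through.** **1. The plan's own sample size.** Inputs from section 13.0: difference 12 h, SD 23.7 h, 80% power, two-sided 0.05.

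- Normal approximation: n = 2 × (1.960 + 0.842)² × 23.7² / 12² = 61.2, so 62 per arm.
- The exact t-test solution is 62.2, so 63 per arm (power 80.5%). Then 63 / 0.90 = 70.

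The stated 63 and 70 reproduce. The documents give no figure for the Bristol endpoint. I use 63 recorded stools per arm below.

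**2. Does the p-value separate the two ends?** This needs no assumed distribution. The tables are constructed, 63 per arm:

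| Table | Arm | 1 | 2 | 3 | 4 | 5 | 6 | 7 |
|---|---|---|---|---|---|---|---|---|
| A | Control | 12 | 12 | 9 | 9 | 9 | 6 | 6 |
| A | Prunes | 4 | 4 | 17 | 17 | 9 | 6 | 6 |
| B | Control | 6 | 6 | 17 | 17 | 9 | 4 | 4 |
| B | Prunes | 6 | 6 | 9 | 9 | 9 | 12 | 12 |

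- In each table, two columns split 12 and 4 (expected 8). Each contributes 2 × 4²/8 = 4.
- Two columns split 9 and 17 (expected 13). Each contributes 2 × 4²/13 = 2.46.
- The other three contribute 0. The total is 8 + 4.92 = 12.92 on 6 df, p = 0.044, in both tables.
- In A, types 1-2 fall from 24 to 8 and types 6-7 stay at 12 and 12. In B, types 1-2 stay at 12 and 12 and types 6-7 rise from 8 to 24.
- The change is 16/63 = 25.4 points either way. The Wald SE is √(0.381×0.619/63 + 0.127×0.873/63) = 0.074, so the 95% interval is 11 to 40 points, downward in A and upward in B.

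**3. Power against a consistent shift.** Assumed control distribution, types 1 to 7: 15/18/20/25/12/7/3%. The common odds ratio applies to every cumulative split. At an odds ratio of 2:

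- types 1-2: odds 0.33/0.67 = 0.493, halved to 0.246, so 33% becomes 19.8%;
- types 6-7: odds 0.10/0.90 = 0.111, doubled to 0.222, so 10% becomes 18.2%.

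Simulated power at 0.05 (4,000 trials per row):

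| Odds ratio | Chi-square, 7 types | Rank-sum |
|---|---|---|
| 1.5 | 12% | 25% |
| 2.0 | 29% | 58% |
| 2.5 | 53% | 83% |
| 3.0 | 69% | 92% |

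Repeat runs at an odds ratio of 2, including a second control distribution (15/20/20/25/10/6/4%), gave 29-31% for the chi-square and 57-59% for the rank-sum. In these scenarios, including no difference, 86% to 99% of the simulated tables had an expected count below 5.

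**4. What the rank-sum does not do.** On the tables in step 2 it gives p = 0.097 for A and 0.018 for B. Its gain is for a consistent shift. When one end alone moves it can do no better than the chi-square, so separate estimates for the two ends are still needed.

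**5. Precision of those estimates.** Score (Newcombe) intervals at 63 per arm:

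- 10% versus 25%: Wilson limits are 0.048 to 0.199 and 0.160 to 0.369. Lower limit 0.150 − √(0.090² + 0.099²) = 0.016; upper limit 0.150 + √(0.119² + 0.052²) = 0.280. Half-width about 13 points.
- 35% versus 15%: half-width about 15 points by the same method.

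**6. Chance findings.** With no true difference, at least one of the two cuts reaches p < 0.05 about 10% of the time, or about 13% if the chi-square is also read as a test. Searching all six possible cuts afterwards gives about 21%.

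**The case against.** The best defence is that direction is not hidden. The planned comparison is of frequencies by arm, so the counts would presumably be shown, and a reader could see which end moved. That stands. A reader might infer that the trial would be unable to say whether hard stools fell or loose stools rose; the documents do not support this. What is missing is a grouping fixed in advance and an interval. Nor is it a special fault that the p-value is unchanged when the arms are swapped, since that holds for any two-sided comparison.

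It is also tempting to claim that testing each end directly would roughly double power. Under the second control distribution, a rise in types 6-7 from 10% to 25% gives 31% for the planned test and 61% for the matching cut; a fall in types 1-2 from 35% to 15% gives 47% and 75%. But that pairs each scenario with the cut that suits it, unadjusted. At 0.025 per cut the figures are 49% and 64%, against 50% and 67% for a chi-square on types 1-2/3-5/6-7, and the plan does not say whether types would be pooled. Under a common odds ratio of 2, types 6-7 alone have about 25% power, less than the planned test. The case for the two proportions is therefore readability, not power.

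Two further limits stand. The grouping is mine: the form describes only type 1 as hard, and type 2 merely as lumpy. And the form first asks "Have you had a bowel movement since surgery", so a woman without a stool has no Bristol type. How many there would be cannot be settled from the documents, because the background figure of "4 days +/- 1.5 days" is for women without intervention, while controls here take docusate.

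**Conclusion.** The point holds as a modest improvement. The inability of the chi-square p-value to tell one end of the scale from the other is a mathematical fact and needs no assumption. The power loss, about 29% against 57% at a common odds ratio of 2, depends on an assumed control distribution, a consistent shift, seven unpooled types and 63 recorded stools per arm. It shows scale and does not predict this trial.

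A reader might carry this further, to doubt about the main result or to a claim that loose-stool safety would be settled by the change. Neither follows. The primary endpoint and the sample size do not use the Bristol scale. Types 6-7 at the first stool are at most a partial proxy for diarrhea.

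**What to change.** In section 10.0, replace the analysis of endpoint 1 with wording such as:

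*Bristol type of the first stool will be compared between arms by the Wilcoxon rank-sum test; the chi-square on type frequencies will be given as descriptive support. Among women with a recorded first stool, the proportions with types 1-2 and with types 6-7 will be reported by arm, each with a risk difference and 95% score interval, as estimates only. The number of women with no recorded stool and the number using rescue laxatives will be shown by arm alongside.*

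The rank-sum belongs to the non-parametric approach already allowed for endpoints 2 to 4. Everything needed is on the existing forms, so the cost is a few sentences and table rows, with no new item, visit or participant.

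The downsides should be stated with the results: intervals of about 13 to 15 points either side; about a 10% chance that at least one of the two estimates looks nominally significant when nothing differs (about 13% if the chi-square is also read as a test); and a comparison restricted to women who had a stool. That restriction applies equally to the planned test; the no-stool counts make it visible.

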### 3.6 Evaluation Post-Intervention:

1. All participants will record the date and time of, consistency of and pain associated with their first bowel movement, and answer whether they experienced secondary outcomes as described later.

2. Participants in the treatment arm will also log the number of prunes consumed each day.

2. Participants will be given a stamped and addressed envelope to return the data collection sheets in. Participants will receive a call from an investigator masked to the treatment allocation on postoperative day 3 inquiring about whether the participant has mailed the data collection sheets back. Those who do not answer will be called again the next day.

3. During the phone call, if the participant indicates any postoperative concerns, she will be instructed to contact the on call physician at the LAC+USC Ob/Gyn Triage.

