### 8.3 Adverse Event Reporting:

8.31 Patient will be advised to tell study physician if she feels that she has been injured because of taking part in this study.

8.32 The PI will appropriately report all adverse events to the IRB.

8.4 Data Monitoring Committee: All injuries believed by the treating medical doctor to be due to participation in this study will be reviewed by the Data Monitoring Committee of USC.

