### Bristol stool chart

Type 1		Separate hard lumps, like nuts (hard to pass)
Type 2		Sausage-shaped but lumpy
Type 3		Like a sausage but with cracks on its surface
Type 4		Like a sausage or snake, smooth and soft
Type 5		Soft blobs with clear-cut edges (passed easily)
Type 6		Fluffy pieces with ragged edges, a mushy stool
Type 7		Watery, no solid pieces, Entirely liquid

How satisfied were you with the treatments you received to help you with bowel movements after the surgery?

Not at all satisfied 0    1    2    3    4    5    6    7    8    9    10 Extremely satisfied

How satisfied were you with your surgery overall?

Not at all satisfied 0    1    2    3    4    5    6    7    8    9    10 Extremely satisfied

How many docusate did you take on day 1? \_\_\_\_\_

How many docusate did you take on day 2? \_\_\_\_\_

How many docusate did you take on day 3? \_\_\_\_\_

Did you use any laxatives? Yes No

If yes, what? \_\_\_\_\_

If yes, what day? \_\_\_\_\_

If in study group (prunes):

How many prunes did you eat on day 1? \_\_\_\_\_

How many prunes did you eat on day 2? \_\_\_\_\_

How many prunes did you eat on day 3? \_\_\_\_\_

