**Bristol stool chart**

Type 1		Heces en bolas duras y separadas. Como frutos secos.
Type 2		Heces con forma alargada como una salchicha pero con relieves como formada por bolas unidas.
Type 3		Heces con forma alargada como una salchicha, con grietas en la superficie.
Type 4		Heces con forma alargada como una salchicha, lisa y blanda.
Type 5		Heces blandas y a trozos separadas o con bordes defractos.
Type 6		Heces blandas y a trozos separadas o con bordes pegados como mermelada o pure.
Type 7		Heces liquidas sin trozos solidos.

¿Cuán satisfecho estuvo con los tratamientos que recibió para ayudarle con los movimientos intestinales después de la cirugía?

Nada 0 1 2 3 4 5 6 7 8 9 10 Extremadamente  
satisfecho satisfecho

¿Qué tan satisfecho estuvo con su cirugía en general?

Nada 0 1 2 3 4 5 6 7 8 9 10 Extremadamente  
satisfecho satisfecho

¿Cuántos docusate tomó el día 1? \_\_\_\_\_

¿Cuántos docusate tomó el día 2? \_\_\_\_\_

¿Cuántos docusate tomó el día 3? \_\_\_\_\_

¿Utilizó algún laxante?  Sí  No

Si sí, ¿qué? \_\_\_\_\_

Si sí, ¿qué día? \_\_\_\_\_

Si en el grupo de estudio (ciruelas pasas):

¿Cuántas ciruelas comió el día 1? \_\_\_\_\_

¿Cuántas ciruelas pasas comiste el día 2? \_\_\_\_\_

¿Cuántas ciruelas comió el día 3? \_\_\_\_\_

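### Secondary endpoint 8 (extreme bloating or flatulence) has no question on any data form, so its planned chi-square test has no systematically collected data

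*Combined protocol and SAP*

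**What the plan says.** Section 10.0 defines the eighth secondary endpoint as "Adverse events of extreme bloating or flatulence (yes or no, assessed as categorical variables and evaluated by chi-square test". It is the only endpoint there that is labelled an adverse event. Section 8.1, on side effects to be monitored, names flatulence among the effects that prunes may cause.

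On collection, section 3.6 says that all participants will record details of their first bowel movement and "answer whether they experienced secondary outcomes as described later". The contact after discharge is a telephone call: "Participants will receive a call from an investigator masked to the treatment allocation on postoperative day 3". Its stated purpose is to ask whether the data sheets have been mailed, and "if the participant indicates any postoperative concerns, she will be instructed to contact the on call physician".

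Section 8.3 sets the adverse-event route: "Patient will be advised to tell study physician if she feels that she has been injured" because of the study, and "The PI will appropriately report all adverse events to the IRB".

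The forms are in Appendices III to V. The survey asks direct questions about the other secondary endpoints. For laxative use, for example, it has "Did you use any laxatives? Yes No", and the Spanish version has the matching question "Utilizó algún laxante".

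**The concern.** A chi-square comparison of a yes/no endpoint needs a recorded yes or no for each participant, obtained in the same way in both arms. Section 3.6 promises that participants will be asked, but the forms that carry out the promise leave this endpoint out.

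If the forms are used as written, the analyst has two choices. The value can be treated as missing for nearly everyone, which leaves nothing to test. Or the absence of a report can be read as no, which understates how often the symptom occurred.

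The second choice also risks bias between arms. Participants know whether they were given prunes, so those in the prune arm may be more ready, or less ready, to mention gas. What is at stake is the trial's only adverse-event endpoint, and so what it can say about the tolerability of the intervention.

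**Working it through.** **Step 1. Match each secondary endpoint in section 10.0 to an item in Appendix III.**

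| Endpoint | Item on the self-administered survey | English | Spanish |
|---|---|---|---|
| 1 Stool consistency | Bristol type, circle 1 to 7 | yes | yes |
| 2 Pain with bowel movement | 0 to 10 scale | yes | yes |
| 3 Satisfaction with bowel regimen | 0 to 10 scale | yes | yes |
| 4 Satisfaction with surgery | 0 to 10 scale | yes | yes |
| 5 Laxative requirement | yes/no, with what and which day | yes | yes |
| 6 Docusate compliance | counts for days 1, 2 and 3 | yes | yes |
| 7 Prune compliance | counts for days 1, 2 and 3 | yes | yes |
| 8 Extreme bloating or flatulence | none | no | no |

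Result: 7 of 8 have an item.

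**Step 2. Look for endpoint 8 on the remaining forms.** The screening, baseline and randomization sheets record eligibility, baseline and operative data. The day 3 sheet, as extracted, holds the day and time of discharge. The diaries in Appendices IV and V record when prunes and stool softener were taken. None asks about bloating, flatulence or adverse events.

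**Step 3. Look for another systematic source.**
- The call in section 3.6 is described as a check on mailing, with concerns referred elsewhere. No symptom question is described.
- Section 8.3 depends on a participant deciding that she has been injured. A woman with severe gas may not see herself that way.
- Reporting to the IRB passes on events already known and does not ask each participant.
- Section 12.1 describes transcribing the data sheets into the database, which adds no new source.

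So none of the planned 70 + 70 = 140 participants has a yes/no value from a planned form.

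**Step 4. Illustrate what reading silence as no would do.** The plan gives no event rate, capture rate or power for endpoint 8, so every rate below is an assumption. Let p be the true rate in an arm and f the fraction of events that are volunteered, equal in both arms. The observed rate is f × p, and the observed difference is f × (p in the prune arm − p in the control arm). Power is exact for the uncorrected Pearson chi-square test, two-sided 0.05, with 63 analysed per arm (the number in section 13.0 before inflation for attrition).

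| Assumed true rates, prunes vs control | f = 100% | f = 50% | f = 25% |
|---|---|---|---|
| 30% vs 10%: observed difference | 20 points | 10 points | 5 points |
| 30% vs 10%: power | 0.82 | 0.48 | 0.24 |
| 20% vs 10%: power | 0.34 | 0.18 | 0.10 |
| 40% vs 20%: power | 0.70 | 0.34 | 0.18 |

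**Step 5. Unequal capture.** If f differs by arm, the error can go the other way. Suppose the true rate is 20% in both arms, and half of the events are volunteered with prunes but a quarter without. The observed rates are 0.50 × 20% = 10% and 0.25 × 20% = 5%, so a 5-point difference appears where none exists.

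**The case against.** The strongest reply is that section 3.6 already commits the trial to asking about secondary outcomes, so this is a line left off a form and not a flaw in the design. That describes the gap fairly: the text and the forms disagree. But the forms are what participants fill in, and the commitment is not met for this endpoint.

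A second reply is that the forms may not be fully visible. The day 3 sheet is sparse in the available text, and some pages were removed before review; from the list of appendices these appear to be consent and contact pages. A lost item on the day 3 sheet cannot be ruled out. However, the survey, where the other seven endpoints sit, looks complete, and its English and Spanish versions agree in leaving this item out.

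A third reply concerns size. The trial was powered for time to first bowel movement and claims no power for endpoint 8. The rates in the illustration are invented, and in two of the three scenarios power is below 80% even with full capture. This is correct. The loss of power shows a mechanism and is not an estimate, and the concern does not depend on it.

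Two smaller points also have some force. Section 8.1 speaks of mild, passing flatulence, whereas the endpoint concerns extreme symptoms, and bloating is not named there. Also, a survey mailed before the day 3 call may not cover all of day 3. That limit already applies to the existing docusate and prune counts for days 1 to 3.

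**Conclusion.** The concern holds. Endpoint 8 is the only one of the eight secondary endpoints without a survey item, and no other planned source yields a yes/no value for each participant. The planned test therefore cannot be done on systematically collected data. Some volunteered reports may arise, but a missing report cannot be read as no.

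The consequence is confined to this endpoint; the primary endpoint and the other seven secondary endpoints are untouched. The change should be made because this is the trial's only adverse-event endpoint.

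The conclusion rests on reading the forms, with one assumption: that no item was lost from the sparse day 3 sheet or the removed pages. The effect on the estimate cannot be determined from the documents. Under equal under-reporting the difference shrinks, while under unequal reporting it may shrink or grow.

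**What to change.** Add one yes/no question on extreme bloating or flatulence to the English and Spanish surveys, for both arms.

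- **Definition.** Give a short plain-language meaning of extreme, fixed before enrolment. The documents do not define the word.
- **Recall window.** Ask about the time from randomization, on the morning of postoperative day 1, through day 3, in line with the existing day 1 to 3 items. A window starting at surgery would count symptoms from before randomization. State that the survey should be completed at the end of day 3, so that the window is covered.
- **Mode.** Keep the question on the written survey and out of the masked caller's script, because a conversation about gas could lead a participant to mention prunes. This is a precaution; the plan does not put the question in the call.
- **Analysis.** Treat an unanswered item as missing, not as no.

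If the item is not added, remove endpoint 8 from the tested endpoints and report volunteered events by arm descriptively, stating that they were not solicited.

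The cost is one line on a form that is already mailed back, with no extra visit, staff or participants. The answer remains an unmasked self-report, so different reporting by arm is reduced but not removed.
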